Intralymphatic immunotherapy in pollen-allergic young adults with rhinoconjunctivitis and mild asthma: A randomized trial

Date: 24/11 2019.

Study outline

All eligible allergic patients at the allergy clinics at the Karolinska University Hospital in Solna/Huddinge, Stockholm, Sweden, were screened and enrolled in the study during the inclusion period January 1, 2013, and December 31, 2015. Inclusion criteria were age 16 to 45 years, confirmed allergy to birch and/or timothy grass pollen together with rhinoconjunctivitis and mild asthma (controlled asthma [asthma control test score > 19] and a positive methacholine challenge), and otherwise healthy. Exclusion criteria were troublesome allergy to mites and animal dander, disease in the upper airways including sinusitis and nonallergic rhinitis, uncontrolled asthma, pregnancy, breast-feeding, other illnesses, and drug abuse. Unfortunately, the required number of patients (60 according to the power calculation; see the Statistical Analysis section below) was not reached because of narrow inclusion criteria. The study was randomized, double-blind, placebo-controlled, and performed between 2013 and 2017. Before each treatment period, an assistant prepared sealed opaque envelopes for both active and placebo treatments to achieve a final 1:1 ratio. After the first year of the study, it was revealed that 3 actively treated patients had to be excluded and therefore, patients were randomized 2:1, active:placebo, for the remainder of the study to achieve the 1:1 ratio. The envelopes were randomly mixed, and an independent nurse drew 1 envelope for each patient and prepared the medical product according to the envelope at all 3 injection visits. The active allergen extracts could not be distinguished from placebo. Using this method, all the participants, physicians who administered the interventions, and study staff who evaluated the outcomes remained blinded until the follow-up visit after the first pollen season was completed.

Assessment of clinical parameters

Clinical parameters were evaluated before the start of the treatment, in the fall after the first pollen season, and in the fall after the second pollen season (active group only). Treatment effect was evaluated by asking the patients to compare their allergic symptoms during the last pollen season with the pollen season before treatment on a visual analogue scale ranging from 0 (unchanged symptoms, no improvement) to 10 (total symptom relief, complete recovery). Asthma control 4 weeks before follow-up was estimated with the asthma control test, where a score of 19 or less suggests poorly controlled asthma.^{E1} Quality of life was assessed using the Juniper Asthma Quality of Life Questionnaire, giving a score ranging from 1 to 7, and a change in score of 0.5 points is considered clinically relevant.^{E2} Modified SSs and MSs^{E3} were calculated taking into account the frequency: daily (4 points); every second day (3 points); 1 to 3 days per week (2 points); occasionally (1 point); never (0 points), for the following symptoms: blocked nose, rhinorrhea, fatigue, sneezing, and asthma symptoms, and for the following medications used: local and systemic antihistamines, nasal steroids, asthma medication, and eye drops. A maximum score of 20 points for symptoms and 16 points for medication could be obtained.

Nasal provocation tests (NPTs) were performed with a commercially available birch or grass extract, Aquagen 100,000 SQ-E/mL (ALK-Abelló, Copenhagen, Denmark), according to a modified Lebel protocol.^{E4} One spray dose, 0.1 mL of the extract (10,000 SQ-E), was deposited in each nostril. Symptoms during NPTs were scored according to the Lebel scoring scale before and 5, 15, and 30 minutes after administration by a trained research nurse. The scoring system identifies nasal, eye, and ear symptoms: rhinorrhea, nasal pruritus, nasal congestion, ocular pruritus, watery eyes, and itchy ears, each graded on a scale from 0 to 3

points, and a total score was summarized after subtracting the starting score (maximum score is 54 + the number of sneezes).

Fraction of exhaled nitric oxide, FEV₁, and forced vital capacity were measured according to international guidelines.^{E5} Bronchial hyperresponsiveness to a challenge with methacholine was assessed, and the dose of methacholine causing a 20% reduction in FEV₁ (PD₂₀) was calculated.^{E6}

Assessment of serum antibodies

Blood was taken at each visit, and serum and plasma were collected for immunological analyses. Allergen-specific IgE level was measured by ImmunoCAP (Phadia, Thermo Scientific, Uppsala, Sweden) for birch (t3) and timothy grass (g6) pollen according to the manufacturer's instructions. A cutoff level ≥ 0.35 kU_A/L was considered positive. In addition, IgG to birch/timothy grass pollen and IgG₄ to birch/timothy grass pollen were measured by ImmunoCAP, with the cutoff 2 mg/L for IgG and 0.05 mg/L for IgG₄.

Outcomes

The primary outcome of the study was the change in symptoms score after NPT. The secondary outcomes were SSs and MSs, changes in response to a bronchial challenge with methacholine (PD₂₀), treatment effect measured on a visual analogue scale, changes in quality of life, changes in allergen-specific serum immunoglobulin levels, incidence of adverse events, changes in asthma symptom scores, changes in pulmonary function measurement (FEV₁ and forced vital capacity), and changes in airway inflammation assessed by fraction of exhaled nitric oxide.

Adverse events and patient analysis

Four patients were removed or left the study before analysis of results; 3 patients (active group) were excluded after the first treatment period because of deviations from the treatment protocol, and 1 patient (placebo) left the study after the first treatment period, before the follow-up (see [Fig E1](#)).

No adrenaline was needed during the study. In total 91 injections were given, 55 with active treatment and 36 with placebo. A total of 69 mild side effects (pain, redness, itch or swelling at injection site, sneezing, and tiredness) within 24 hours after injection were reported. Fifty-nine of these were reported from 13 patients receiving active treatment, and 10 from 5 placebo-treated patients. In the active group, 1 patient suffered from generalized urticaria 15 minutes after injection and 1 patient reported increased asthma symptoms the day after injection.

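### The move to 2:1 allocation after year 1, with no stated return to 1:1, ties arm to treatment period; report the ratio obtained and add a post hoc period-adjusted comparison

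*Combined protocol and SAP*

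**What the plan says.** All references are to the combined protocol and SAP.

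- **Study outline, allocation target:** "Before each treatment period, an assistant prepared sealed opaque envelopes for both active and placebo treatments to achieve a final 1:1 ratio".
- **Study outline, change after year 1:** "patients were randomized 2:1, active:placebo, for the remainder of the study to achieve the 1:1 ratio". The reason given is the exclusion of 3 actively treated patients. No point of return to 1:1 is stated.
- **Study outline, size and timing:** patients were enrolled "during the inclusion period January 1, 2013, and December 31, 2015", and "the required number of patients (60 according to the power calculation; see the Statistical Analysis section below) was not reached".
- **Study outline, dosing visits:** a nurse "prepared the medical product according to the envelope at all 3 injection visits".
- **Adverse events and patient analysis:** "3 patients (active group) were excluded after the first treatment period because of deviations from the treatment protocol". One placebo patient also left after the first treatment period. Injections numbered 91 in total, 55 active and 36 placebo.
- **Assessment of clinical parameters:** for the VAS, patients were asked to "compare their allergic symptoms during the last pollen season with the pollen season before treatment".
- **Outcomes:** "The primary outcome of the study was the change in symptoms score after NPT". Symptom and medication scores and the VAS are secondary.

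The Statistical Analysis section and Fig E1 are cited, but they are not in the text available for this review.

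**The concern.** A 2:1 ratio repairs a shortfall of 3 active patients only up to a point. Kept to the end of enrolment, it overshoots and produces an active excess. That costs little power.

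The more important consequence is that the ratio differs between year 1 and later, and the exclusions thin the year-1 active group further. Placebo patients therefore come disproportionately from year 1, and active patients from later periods. Symptom score, medication score and the season-against-season VAS depend on how heavy the pollen was in the year concerned. If periods are pooled crudely, part of any year difference is read as a treatment difference.

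The nasal provocation outcome uses a fixed extract dose. It is exposed only indirectly, for example through drift between years in scoring or in the extract.

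**Working it through.** **Inputs.** Stated: 55 active and 36 placebo injections (55 + 36 = 91, agreeing with the stated total); 3 injection visits; losses of 3 active and 1 placebo; 2:1 after year 1. Assumed: one injection per visit, complete placebo courses, and year 1 within one patient of balance.

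**Parity point.** Exact 2:1 gains one active patient per 3 enrolled. A shortfall of 3 closes after 3 × 3 = 9 patients. If the placebo leaver is counted the shortfall is 2, and it closes after 6.

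**Patient numbers.** Active: 55/3 = 18.3, so at least 19. Placebo: 36/3 = 12. After losses: 19 − 3 = 16 and 12 − 1 = 11. If the lost patients are outside the injection counts, 19 v 12 were analysed. Because 55 is not a multiple of 3, at least one active course was incomplete. Parity with 16 analysed active patients would need 16 or 17 placebo patients averaging 36/16 = 2.25 or 36/17 = 2.12 injections each. Under plain 1:1 allocation, P(19 or more active of 31) = 0.14, so chance is not excluded.

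**Share of a year effect in a crude contrast.** With a1 active and p1 placebo patients allocated in year 1, and the stated losses taken from year 1:

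share = (p1 − 1)/11 − (a1 − 3)/16

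| Year 1 | Later | Analysed, year 1 | Share |
|---|---|---|---|
| 5:5 | 14:7 (exact 2:1) | 2 v 4 | 4/11 − 2/16 = 24% |
| 7:6 | 12:6 (exact 2:1) | 4 v 5 | 5/11 − 4/16 = 20% |
| 3:4 | 16:8 (exact 2:1) | 0 v 3 | 3/11 − 0 = 27% |
| 4:3 | 15:9 | 1 v 2 | 2/11 − 1/16 = 12% |
| 6:7 | 13:5 | 3 v 6 | 6/11 − 3/16 = 36% |

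The last two rows let the realised later ratio differ from exactly 2:1. The range is not a hard bound: 3:2 then 16:10 gives 1/11 − 0 = 9%. If the losses are outside the counts, exact 2:1 splits give 18–20%.

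**What this means on an outcome.** No year effect is given in the documents. For an assumed 2-point year difference on the 0–10 VAS, the contrast would shift by 2 × 0.24 = 0.48 points in the 5:5 case, and by 2 × 0.12 = 0.24 to 2 × 0.36 = 0.72 over the table.

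**Type I error** (simulated crude t-test at 5%, no treatment effect). The 5:5 case gives about 5.5% at a year effect of 0.5 SD and 6.7% at 1 SD. Over the three exact 2:1 splits it is about 5–6% and 5–9%; a larger share would give more. With a period factor it is about 5% throughout.

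**Cost of adjusting** (variance in SD² units, 5:5 case).
- Crude: 1/16 + 1/11 = 0.1534.
- Within period: 1/(2×4/6 + 14×7/21) = 0.1667.
- Ratio: 1.09. It is 1.22 for 3:4, and for 4:3 then 15:9 it is [1/(1×2/3 + 15×9/24)]/0.1534 = 0.1589/0.1534 = 1.04.
- On squared bias plus variance, adjustment gains only above a year effect of √(0.1667 − 0.1534)/0.239 ≈ 0.48 SD.

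**Cost of the imbalance alone.** Efficiency relative to an equal split is 4×16×11/27² = 0.966, or 4×19×12/31² = 0.949.

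**The case against.** **The counts rest on an unstated premise.** The text gives 3 injection visits but does not say one injection per visit, and patients could be allergic to both pollens. This stands. One per visit is the natural reading, but it is an assumption under every patient number above.

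**The envelopes were prepared per period with a final 1:1 in view, so a return to 1:1 may have been possible.** This stands in part: an unstated stop cannot be excluded. The injection counts nevertheless fit 2:1 kept past parity better than they fit 1:1. Nor does the enrolment shortfall readily explain an excess. If 60 were allocated, with 5:5 in year 1 and 2:1 kept throughout, the totals would be 5 + 50×2/3 = 38 v 5 + 50/3 = 22 before losses.

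**The wording about achieving 1:1 states a purpose, not a result.** Correct. It should be supplemented, not removed.

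**The effect is small and the remedy late.** Type I inflation is modest, and adjustment can cost more than it saves when the year effect is small. The document is dated November 2019 for a study performed in 2013–2017, and it already reports adverse events by arm. An adjusted analysis added now is post hoc and must be labelled so.

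**Readings that go too far.** A reader might infer that the randomisation was faulty, that failure to reach 1:1 is established, or that the analysis ignores period. The documents support none of these. Chance and incomplete courses remain possible, Fig E1 may give the disposition, and the Statistical Analysis section could not be read.

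**Conclusion.** The point holds in a limited form. The association between arm and treatment period follows from two stated facts, the ratio change and the year-1 active exclusions, given a year 1 near the 1:1 target. It does not depend on the injection arithmetic; only its size does.

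Under one injection per visit, complete placebo courses and losses from year 1, a crude contrast carries roughly 12–36% of any year effect, with 24% as the central illustration. The damage depends on a year effect that the documents do not give. It concerns mainly symptom score, medication score and VAS. A reader might infer that the primary nasal provocation result is biased; with a fixed extract dose the documents give no direct route for that. Departure from 1:1 is suggested, not proven, and lost efficiency is not the issue.

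**What to change.** 1. **Reporting.** Keep the stated reason for moving to 2:1. Add the ratio actually obtained, with numbers allocated and analysed by arm and treatment period, unless Fig E1 already shows them. This takes one sentence or a small table.

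2. **Season-dependent secondary outcomes.** Unless the Statistical Analysis section already compares arms within period, add a period-adjusted comparison for symptom score, medication score and VAS. Use a year-1-versus-later factor in a linear model (with baseline as covariate where one exists), or a van Elteren test stratified by period. Label it post hoc and report it beside the planned analysis.

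3. **Primary outcome.** Leave the planned nasal provocation analysis as it is, and add the period-adjusted version as a sensitivity analysis only.

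No new data are needed. The price is 1 df (2 if each of the three inclusion years is a period) and roughly 4–22% more variance in the treatment estimate. If no active year-1 patient remains, as in the 3:4 case, adjustment amounts to setting year 1 aside, and the report should say so.

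### Allocation as described is not balanced on birch versus grass, although the primary nasal provocation uses one extract or the other; tabulate and adjust for challenge allergen.

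*Combined protocol and SAP*

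**What the plan says.** **Study outline.** Eligible patients have "confirmed allergy to birch and/or timothy grass pollen together with rhinoconjunctivitis and mild asthma", so the trial mixes birch-allergic, grass-allergic and doubly allergic patients. On allocation: "Before each treatment period, an assistant prepared sealed opaque envelopes for both active and placebo treatments to achieve a final 1:1 ratio". Then: "The envelopes were randomly mixed, and an independent nurse drew 1 envelope for each patient". After the first year, "patients were randomized 2:1, active:placebo, for the remainder of the study to achieve the 1:1 ratio". The envelopes are described only as active or placebo. No strata, blocks or separate birch and grass sets are mentioned. On size, "the required number of patients (60 according to the power calculation; see the Statistical Analysis section below) was not reached".

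**Assessment of clinical parameters.** "Nasal provocation tests (NPTs) were performed with a commercially available birch or grass extract". Both extracts have the same labelled strength, and symptoms are scored on one common scale.

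**Outcomes.** "The primary outcome of the study was the change in symptoms score after NPT".

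The documents do not give the number of patients challenged with each extract, or say which extract a patient allergic to both pollens received.

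**The concern.** The extract used at challenge partly determines what the primary endpoint measures, and a patient's allergy is known before the envelope is drawn. The allocation as described does nothing to hold the arms alike on that factor. In a large trial this would hardly matter. This one stopped well short of its planned 60, so a visible difference between the arms in birch share can arise by chance.

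If NPT scores change differently over the study in birch and grass patients, whatever their treatment, part of that difference would enter the treatment comparison. It could enlarge the apparent effect or mask it. Without a table of allergen by arm, a reader cannot tell whether this happened.

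**Working it through.** **The plan's own figure.** The required 60 cannot be reproduced, because the available text gives no alpha, power, effect size or SD. As an illustration only, 30 per arm at two-sided 0.05 corresponds to a standardised effect of (1.960 + 0.842) × √(2/30) = 0.72 at 80% power, or 0.84 at 90%. Nothing below depends on it.

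**Arm sizes (inferred).** Adverse events and patient analysis reports 55 active and 36 placebo injections; Study outline gives three injection visits.
- Active: 55/3 = 18.3, so at least 19 patients.
- Placebo: 36/3 = 12, so at least 12.
- After the three active exclusions and one placebo withdrawal: about 16 v 11.

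**Allergen split (assumed).** Let K be the number challenged with birch. It is not stated, so it is varied.

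**Formula.** Under unstratified allocation, the number X of birch patients in the active arm is hypergeometric (N = 31, K birch, 19 drawn). The gap in birch share is X/19 − (K − X)/12.

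**Worked case, K = 16.** The gap is at least 20 points in size when X ≤ 8 (at X = 8: 8/19 − 8/12 = −24.6 points) or X ≥ 12 (at X = 12: 12/19 − 4/12 = +29.8 points). The two tails are 0.168 and 0.106, together 0.27. For at least 30 points (X ≤ 7 or X ≥ 13) the total is 0.07.

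**Over a range of splits.**

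| Arms | K | P(gap ≥ 20 points) | P(gap ≥ 30 points) |
|---|---|---|---|
| 19 v 12 | 6 to 25, except 9 and 22 | 17-29% | 3-14% |
| 18 v 12 | 9, 15, 21 | 25-26% | 6-10% |
| 16 v 11 | 8, 14, 19 | 21-25% | 9-12% |
| 30 v 30 (planned) | 18, 30, 42 | 16-20% | 1-2% |

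These probabilities jump because patients come in whole numbers. At 19 v 12 with K = 9 or 22, and at some counts for 16 v 11, the 20-point figure rises to 41-43%; the reason is under the objection.

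**Smooth check.** The SD of the gap is about √[p(1 − p)(1/19 + 1/12)]. This is 16.9 points at p = 0.3 and 18.4 at p = 0.5. The normal approximation then gives P(gap ≥ 20) of 24% and 28%. For 16 v 11 the SDs are 17.9 and 19.6 points, giving 26-31%. About one in four is therefore a fair summary.

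**Effect on the estimate.** If mean NPT change differs by d points between birch and grass patients in the same way in both arms, a gap g shifts the unadjusted treatment difference by g × d. For g = 0.20 this is 0.2d. As assumed values only: d = 1, 3 or 5 points gives 0.2, 0.6 or 1.0 points.

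**What stratification would have done.** This was simulated with assumed period sizes (12 patients at 1:1, then 19 at 2:1) and birch shares of 30-70%. One pool per period gave a gap of at least 20 points in 25-27% of randomisations. Permuted blocks within allergen (size 4, then 3) gave under 0.5%.

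**The case against.** **No harm is demonstrated.** The primary outcome is a change, and each NPT total already has its starting score subtracted. The two extracts are given at equal labelled strength. A stable difference in reactivity would therefore largely cancel, and only a difference in change matters. The documents offer no evidence of one. This stands: d is unknown and could be close to zero.

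**Chance imbalance is not bias.** Randomisation remains valid and the unconditional type I error is not raised. This also stands. The issue is precision and how to read this one estimate.

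**The text is silent rather than explicit.** A single pool is inferred. Separate sets are not ruled out, and allergen adjustment may be in the Statistical Analysis section. Neither can be called absent.

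**Not stratifying is defensible** in a trial this small, particularly with a change of ratio and doubly allergic patients who fit neither stratum cleanly. That is reasonable, but it does not count against a one-factor adjustment.

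A reader might also infer three stronger things that the documents do not support:
- *That a 20-point gap has a probability of about 42%.* At 19 v 12 this arises only with 9 or 22 birch patients. With 9, two attainable gaps (20.2 and 20.6 points, probabilities 0.165 and 0.152) fall just over the threshold. Moving it to 21 points cuts the figure to 10%.
- *That a moderate imbalance is to be expected.* About three randomisations in four stay below 20 points.
- *That the symptom, medication and visual analogue scores are distorted by differing birch and grass seasons or pollen loads.* The documents say nothing about such differences.

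**Conclusion.** The point holds as a minor one. Allocation as described does not balance a factor that determines how the primary endpoint is measured. At the size reached, a gap in birch share of at least 20 points has a probability of roughly one in four, and of at least 30 points about 3-14%. The consequence is added noise and a possible shift of 0.2d per 20-point gap, with d unknown. It does not invalidate the randomisation.

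The conclusion rests on arm sizes inferred from injection counts (55 is not a multiple of three, so the arms could be slightly larger), on an assumed allergen split, and on reading the envelope description as one pool per treatment period.

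**What to change.** 1. Tabulate the challenge extract (birch or grass) by arm, for all randomised patients and for those analysed. State which extract doubly allergic patients received, and whether envelopes were kept separate by allergen.
2. Include challenge extract as a two-level factor in the between-arm comparison of NPT change, at least as a sensitivity analysis beside the unadjusted result. If the Statistical Analysis section already does this, only the table is needed.
3. Enrolment is closed, so design-stage stratification can apply only to any further randomisation: separate envelope pools by challenge allergen, with the allergen fixed before the draw and envelopes prepared in small blocks. Without small blocks, partly used pools would lose some of the balance.

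The analysis change costs about one degree of freedom and uses information that must exist for every patient challenged. Stratifying further, for example by clinic as well, would leave strata too small to be useful.

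### Blinding is promised only up to the first-season follow-up in a trial with staggered entry, so assessor blinding of the nurse-scored nasal provocation test is not assured for later cohorts

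*Combined protocol and SAP*

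**What the plan says.** The Study outline describes staggered entry: patients were "enrolled in the study during the inclusion period January 1, 2013, and December 31, 2015", the study was "performed between 2013 and 2017", and "Before each treatment period, an assistant prepared sealed opaque envelopes". An independent nurse drew one envelope per patient and prepared the injections; active and placebo products are stated to be indistinguishable.

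The same section sets the end of blinding. Patients, injecting physicians and outcome assessors "remained blinded until the follow-up visit after the first pollen season was completed".

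Two statements show arm information in use while the trial was running:

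- Study outline: "After the first year of the study, it was revealed that 3 actively treated patients had to be excluded". Randomization then moved to 2:1, active to placebo, for everyone still to be entered.
- Assessment of clinical parameters: besides the baseline and first-fall assessments there is one "in the fall after the second pollen season (active group only".

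The primary outcome (Outcomes) is the change in NPT symptom score. Under Assessment of clinical parameters, a trained research nurse grades each symptom from 0 to 3. Side effects by arm are given under Adverse events and patient analysis: "Fifty-nine of these were reported from 13 patients receiving active treatment, and 10 from 5 placebo-treated patients".

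**The concern.** In a trial with one intake, opening the code after the first-season visit would leave the primary outcome blind. With several intakes, one cohort's first-season visit comes before another's. If staff who score the NPT learn the arms of an earlier cohort, they can link those arms to the reactions they saw. If they also know that the ratio has become 2:1, they can guess later allocations better than by chance.

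The primary outcome depends on an observer's grading, so a scorer's expectation could move it. Several secondary outcomes (visual analogue scale, quality of life, symptom and medication scores) are patient-reported. Others, such as PD₂₀, immunoglobulins, FEV₁ and exhaled nitric oxide, are measurements and less open to this. At stake is how far the double-blind claim reaches beyond the first cohort.

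**Working it through.** The plan gives no figure to reproduce on this point. The check has two parts: the order of events, and what the side-effect counts can and cannot show.

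**1. Order of events**

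- The ratio change applies only to patients randomized after year 1. All of them had their primary NPT after three earlier patients had been identified as active.
- A cohort with first pollen season in year *y* has its primary NPT in fall *y* and its active-only visit in fall *y* + 1. With yearly cohorts, fall *y* + 1 is also the primary-NPT fall of the next cohort.
- If the first season was 2013, the first cohort's active-only visit was in fall 2014; if 2014, in fall 2015.
- Patients included up to the end of 2015 could have a first season in 2016 and a primary NPT in fall 2016. Their second fall would be 2017, which fits the stated end of the study.
- On the tightest reading (first cohort 2014, last first season 2015), the first cohort's active-only visits and the last primary NPTs share fall 2015. The order of visits within a fall is not given.

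So earlier arms were known to someone before or during the fall of later primary NPTs. The documents do not say who that was.

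**2. Side effects as a clue to allocation**

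Inputs, from Adverse events and patient analysis: 55 active and 36 placebo injections (55 + 36 = 91, as stated); 59 and 10 mild side effects (59 + 10 = 69, as stated); 13 active and 5 placebo patients with any side effect.

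- Rate per injection: 59/55 = 1.07 active, 10/36 = 0.28 placebo; ratio 1.073/0.278 = 3.9.
- Reports per reacting patient: 59/13 = 4.5 and 10/5 = 2.0.

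Patient denominators by arm are not given. At three injections each, 55/3 = 18.3 and 36/3 = 12, so I assume 19 to 21 active and 12 to 13 placebo patients.

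*Any reaction.* With 19 and 12 patients, 13/19 = 0.684 and 5/12 = 0.417 reacted. By Bayes' rule, the chance that a reacting patient is active is:

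- at 2:1: 0.667 × 0.684 / (0.667 × 0.684 + 0.333 × 0.417) = 0.77; range 0.75 to 0.78 over the assumed denominators, against a prior of 0.67;
- at 1:1: 0.684 / (0.684 + 0.417) = 0.62; range 0.60 to 0.64, against a prior of 0.50.

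*Three or more reactions.* Negative binomial counts with means 59/19 = 3.11 and 10/12 = 0.83, and dispersion fitted to the shares without a reaction (6/19 and 7/12), give P(≥3) = 0.393 active and 0.102 placebo. Then:

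- at 2:1: 2 × 0.393 / (2 × 0.393 + 0.102) = 0.88; range 0.87 to 0.89;
- at 1:1: 0.393 / (0.393 + 0.102) = 0.79; range 0.77 to 0.81.

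Having any reaction is modestly informative; having several is more so. These figures come from the side-effect imbalance and the allocation ratio. They would be the same if no code had been opened early, so they do not measure the harm from the rule.

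**The case against.** The strongest reply is that nothing places the codes in the scorers' hands. The assistant who made the envelopes and the independent nurse who drew them could have supplied the arms both for the ratio change and for the active-only invitations. The documents do not say whether whole cohorts were opened at once, whether the NPT nurse saw any code, or whether the same nurse scored every cohort. Knowing earlier arms does not open later envelopes, which were randomly mixed. Nor is it stated that NPT scorers saw reaction reports: the side effects fell within 24 hours of injection, and the NPT is in the fall. All of this stands.

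It rules out three stronger readings that a reader might draw:

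- *Later outcomes were scored by staff who knew earlier allocations.* The documents show that someone knew, not that the scorers did.
- *Assessor blinding held for the first cohort and failed afterwards.* Neither half is shown. The three exclusions surfaced after the first year, and the text does not say whether that was before or after the first cohort's NPTs.
- *The 67% success of always guessing active at 2:1, or the 0.88 above, measures the damage.* Guessing active for everyone is the same in both arms and alone cannot bias the difference between them. The 0.88 also rests on whole-trial totals, a chosen threshold and a scorer who knew the reactions.

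What the reply does not remove is that the only stated protection ends at the first-season visit, and no text extends it to later cohorts' scoring.

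**Conclusion.** The concern holds as a gap in assurance. In a trial with several intakes, the rule should protect the scorer until the last primary NPT, and as written it does not. Earlier arms were in use in that interval, as the year-1 disclosure, the 2:1 switch and the active-only visit show. For an observer-graded primary outcome this is worth correcting, but it is no evidence that the result is biased.

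The size is limited to two statements. Side effects were 3.9 times as frequent per active injection as per placebo injection, so allocation could be guessed by anyone who knew a patient's reactions. No bias in NPT points can be derived from the documents. The timing argument assumes roughly yearly cohorts, since the number and dates of the treatment periods are not stated. The probabilities rest on assumed patient denominators and, for three or more reactions, on the fitted count model.

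**What to change.** **The rule.** Allocation, the ratio change and reaction reports stay hidden from NPT scorers and other outcome staff until the last cohort's first-season NPT has been scored and locked. The independent nurse or assistant alone handles ratio changes and second-visit scheduling. Second-fall visits of earlier cohorts are arranged so that they do not reveal arms to staff who still have primary NPTs to score. Inviting both arms would also achieve this, but needs extra placebo visits.

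**What can still be done.** The document is dated 2019 and describes a completed trial, so the rule now serves as a correction to the design. The report should:

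- state who was unblinded, when and for which cohort;
- state whether NPT scorers knew earlier codes, the 2:1 ratio or patients' reactions;
- show the NPT effect before and after the 2:1 switch, as description only. The numbers are small, and three active patients and one placebo patient were lost after the first treatment period, so this split cannot test for bias;
- limit the double-blind claim for later cohorts if scorers had access.

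**Cost.** In the design, later disclosure to early cohorts and some scheduling work. In the report, no new patient data, only a record of who held the codes and one descriptive table.
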